4.6.1.1. Safety Run-in and Part 2, Arm A (Plamotamab, Tafasitamab and Lenalidomide)

Plamotamab is known to cause CRS. CRS has not been observed in clinical trials of tafasitamab and lenalidomide. However, lenalidomide, through its potential to activate T cells, may potentiate CRS in combination with plamotamab. In addition, to avoid the overlap of CRS caused by plamotamab with tafasitamab-induced, infusion-related reactions, plamotamab must always be given after tafasitamab if administered on the same day. See Section 4.7 for dose modification of lenalidomide and plamotamab in the instance of CRS.

4.6.1.2. Part 2, Arm B (Tafasitamab and Lenalidomide)

CRS has not been observed in clinical trials of tafasitamab and lenalidomide. If CRS is observed with tafasitamab, follow treatment guidelines provided for plamotamab and contact the medical monitor as soon as possible.

4.6.1.3. Cytokine Release Syndrome Versus Allergic/ Hypersensitivity/ Infusion-related Reactions

CRS is mechanistically different from allergic/hypersensitive/Infusion-related reactions (Brennan, 2010), although some of the manifestations are common to both AEs and both have been reported to occur with therapeutic antibodies. It is less clear how cytokine release is triggered, although it is likely to be associated with immune cell activation; in this case, CD3-expressing lymphocytes may be the prime effector of CRS. See Section 4.6.2 for management of allergic/hypersensitive/infusion-related reactions.

4.6.1.4. Management of Cytokine Release Syndrome

Management of CRS should be per standard investigational site procedures. Alternatively, if there are no local standards or if they are incomplete, the approaches discussed below may be used.

Contact the Xencor Medical Monitor immediately if questions arise concerning the management of an infusion reaction/CRS/neurotoxicity.

Medical Monitor's contact information:

[REDACTED]
Telephone: [REDACTED]
E-mail: [REDACTED]

4.6.1.4.1. Use of Tocilizumab for Cytokine Release Syndrome

Tocilizumab (Acterna[®]) is a therapeutic antibody that interferes with the binding of interleukin-6 (IL-6) to the IL-6 receptor. It has been used to decrease the severity and, possibly, the mortality of severe CRS (Frey, 2017), and early administration may be useful in improving outcomes. Suggested guidelines for its use are in Section 4.6.1.6, in addition:

- Have sufficient tocilizumab (dose of 8 mg/kg) readily available to the area where subjects are receiving their infusions and being observed post-infusion.
- Repeat dosing of tocilizumab may be necessary if signs and symptoms persist or return after initial treatment

Tocilizumab is the preferred IL-6 antagonist, however, if tocilizumab is unavailable either regionally or due to limited supply, follow institutional or local guidelines for the treatment of CRS until tocilizumab is available.

4.6.1.5. Fluid Management

CRS is sometimes associated with myocardial dysfunction, pulmonary edema, or capillary leak syndrome (Shimabukuro-Vornhagen, 2018). Although there are little or no data regarding use of anti-CD3 antibodies and the need for fluid management, it seems prudent to monitor subjects for weight gain and limit intravenous (IV) fluid administration in the acute setting. Following are guidelines for managing fluids:

- If a subject is noted to have had a $\geq 10\%$ increase in body weight over the previous 2 weeks in association with new or significantly increased bilateral lower extremity edema, delay dosing until this finding is evaluated and, if indicated, treated.
- For acute hypotension, limit an IV fluid bolus to 500 to 1000 mL of normal saline or the equivalent.
- If there is not an adequate response to fluids, consider treatment with tocilizumab (and vasopressors, if necessary) rather than additional fluid boluses.

4.6.1.6. Cytokine Release Syndrome Treatment Guidelines by ASTCT CRS Consensus Grade

The CRS treatment guidelines are listed below by grade:

Grade 1

- Symptomatic management is recommended. Administer acetaminophen 650 mg orally as an antipyretic or analgesic and/or diphenhydramine 25 to 50 mg intravenously or orally for rash, pruritus, or other signs and symptoms of hypersensitivity (allergic) reaction if clinically indicated.
- Measure vital signs every 15 minutes or less, as clinically indicated.
- Obtain an unscheduled blood sample for cytokine analysis during the event and approximately 4 hours later, unless scheduled cytokine monitoring is already in progress on the same visit day.
- Monitor the subject for worsening of condition; if severity of event increases to a higher grade, stop the infusion, administer steroids as above, and refer to guidelines below for more severe reactions.

Grade 2

- Hypotension responsive to fluids not requiring a vasopressor, or mild respiratory symptoms treatable with low-flow oxygen, are signs of Grade 2 toxicity. Older subjects or those with significant comorbidities may be at a higher risk of decompensation in this situation.
- Discontinue the infusion and consider administration of additional dexamethasone at a dose of 10 to 20 mg intravenously; acetaminophen 650 mg orally and/or diphenhydramine 25 to 50 mg intravenously or orally may also be given to treat signs and symptoms.
- Once symptoms have resolved, restart the infusion at 50% of the baseline rate. If after 1 hour, the subject's symptoms do not return and vital signs are stable, the infusion rate may be increased every 30 minutes as tolerated to the baseline rate.

- Measure vital signs every 15 minutes or less as clinically indicated. For subjects who can tolerate an increase in the infusion rate back to baseline and maintain normal blood pressure for 30 minutes after the rate increase then, at the discretion of the Investigator, the frequency of vital sign assessment may be reduced to every 30 minutes during the infusion.
- Obtain an unscheduled blood sample for cytokine analysis during the event and approximately 4 hours later, unless scheduled cytokine monitoring is already in progress on the same visit day.
- Monitor the subject for worsening of condition; if severity of event increases to a higher grade, stop the infusion, administer appropriate treatment, and refer to guidelines below for Grades 3 and 4 reactions.
- Note that older subjects or those with significant comorbidities may be at higher risk of decompensation in this situation. When reactions occur in these vulnerable subjects, or in the case of rapidly progressing reactions, consider treatment with tocilizumab 8 mg/kg IV over 1 hour, with or without additional dexamethasone 10 to 20 mg IV (or equivalent).

Grade 3 and 4

- Stop the infusion and disconnect the infusion tubing from the subject.
- Administer additional dexamethasone 10 mg intravenously.
- Immediately give aggressive supportive care. Use pressors, fluids, oxygen, epinephrine or bronchodilators, ventilatory support, antipyretics, and analgesics as indicated.
- Treatment with tocilizumab, 8 mg/kg IV over 1 hour ([Hallek, 2018](#)), is encouraged for CRS due to the high risk of progression and permanent organ dysfunction.
- Hospital admission for observations is almost always indicated, usually to an intensive care unit, since an initial appearance of improvement may quickly yield to rapid decompensation.
- Subjects with Grade 3 CRS or infusion reaction may be rechallenged once resolved as described in [Section 4.7](#) and [Table 8](#). Subjects with recurrent Grade 3 or any Grade 4 reaction should not receive further plamotamab treatment but will continue to be followed on the protocol (ie, followed for long-term survival).
- Obtain an unscheduled blood sample for cytokine analysis during the event and approximately 4 hours later, unless scheduled cytokine monitoring is already in progress on the same visit day.
- Obtain an unscheduled sample for anti-drug antibodies (ADA) testing as close to the onset of the event as possible, at the resolution of the event, and approximately 28 days

following the event, unless scheduled cytokine monitoring is already in progress on the same visit day.

- Notify the Xencor Medical Monitor immediately.

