Infusion-related reactions	Grade 2 (moderate)	
 • Interrupt infusion of tafasitamab or plamotamab immediately and manage signs and symptoms. • Once signs and symptoms resolve or reduce to Grade 1, resume infusion at no more than 50% of the rate at which the reaction occurred. If the subject does not experience further reaction within 1 hour and vital signs are stable, the infusion rate may be increased every 30 minutes as tolerated to the rate at which the reaction occurred. • Dosing of other study medications is not modified.
	Grade 3 (severe)	
 • Interrupt infusion of tafasitamab or plamotamab immediately and manage signs and symptoms. • Once signs and symptoms resolve or reduce to Grade 1, resume infusion at no more than 25% of the rate at which the reaction occurred. If the subject does not experience further reaction within 1 hour and vital signs are stable, the infusion rate may be increased every 30 minutes as tolerated to a maximum of 50% of the rate at which the reaction occurred. • If the reaction returns after the rechallenge, stop the infusion immediately. • Dosing of other study medications is not modified.
	Grade 4 (life-threatening)	
 • Stop the infusion immediately and permanently discontinue: 
 – Tafasitamab if during or immediately following tafasitamab infusion. – Plamotamab if during or immediately following plamotamab infusion.
Cytokine release syndrome	Grade 2 (moderate)	
 • Interrupt plamotamab infusion immediately and manage signs and symptoms (see Section 4.6.1.6). • Once signs and symptoms resolve or reduce to Grade 1, resume plamotamab infusion at no more than 50% of the rate at which the reaction occurred. If the subject does not experience further reaction within 1 hour and vital signs are stable, the infusion rate may be increased every 30 minutes as tolerated to the rate at which the reaction occurred. • Tafasitamab and lenalidomide dosing is not modified.
	Grade 3 (severe) & Grade 4 (life-threatening)	
 • Interrupt plamotamab infusion immediately and disconnect infusion tubing from subject. Manage signs and symptoms (see Section 4.6.1.6). • The next scheduled dose of plamotamab will be given at 75% of the previous dose, unless the reaction occurred

Adverse Reaction	Severity	Dosage Modification

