		
on the C1D1 dose, in which case 100% of the previous dose may be given.
 
 • For subsequent plamotamab infusions, if: 
 – Toxicity does not recur or recurs at a Grade 1 severity, escalate to full dose of plamotamab at the time of the next dose. – Toxicity recurs at a Grade 2 severity, maintain 75% dosing of plamotamab. – Toxicity recurs at \geq Grade 3 severity at any time or if a Grade 2 takes more than 10 days to resolve to \leq Grade 1, discontinue plamotamab permanently. • Lenalidomide is also modified if a \geq Grade 3 CRS event occurs: 
 – During the first 5 doses of plamotamab: Reduce current dose of lenalidomide by 10 mg (or to 5 mg if currently at 10 mg) for subsequent doses until C4D1, when lenalidomide may be increased back to the dose prior to CRS. If CRS recurs at \geq Grade 2 on subsequent reduced dose lenalidomide, permanently discontinue lenalidomide. – After the first 5 doses of plamotamab: Reduce lenalidomide by 10 mg (or to 5 mg if currently at 10 mg) for all subsequent doses. If CRS recurs at \geq Grade 2 on subsequent reduced dose lenalidomide, permanently discontinue lenalidomide. • Tafasitamab dose is not modified.
Myelosuppression	Platelet count of less than 50,000/ μ L	
 • Withhold plamotamab, tafasitamab, and lenalidomide and monitor CBC weekly until platelet count is 50,000/μL or higher. • Resume plamotamab and tafasitamab at the same dose and lenalidomide at a reduced dose. Refer to lenalidomide prescribing information for dosage modifications. • If recurrence, repeat drug withholding and lenalidomide reduction steps until minimal lenalidomide dose is reached per lenalidomide prescribing information. • If recurrence at minimal lenalidomide dose, repeat drug withholding step (first bullet above) then reduce the next scheduled plamotamab dose to 75% of the previous dose.

Adverse Reaction	Severity	Dosage Modification

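### For a first Grade 4 CRS, Section 4.6.1.6 stops plamotamab for good, while the merged Grade 3 and 4 row of Table 8 gives a next dose

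*Protocol*

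**What the plan says.** Two places in the protocol govern plamotamab after severe CRS.

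**Section 4.6.1.6, Grade 3 and 4.** On rechallenge it says: "Subjects with Grade 3 CRS or infusion reaction may be rechallenged once resolved", with a pointer to Section 4.7 and Table 8. The next sentence is: "Subjects with recurrent Grade 3 or any Grade 4 reaction should not receive further plamotamab treatment".

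**Section 4.7, Table 8.** Grades 3 and 4 CRS share one row with one set of instructions. "The next scheduled dose of plamotamab will be given at 75% of the previous dose, unless the reaction occurred" on C1D1, "in which case 100% of the previous dose may be given". For later infusions the row continues: "Toxicity does not recur or recurs at a Grade 1 severity, escalate to full dose of plamotamab at the time of the next dose". A Grade 2 recurrence keeps the dose at 75%. Permanent discontinuation follows recurrence at Grade 3 or higher "severity at any time or if a Grade 2 takes more than 10 days to resolve to" Grade 1 or below. No bullet singles out Grade 4.

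**Cross-references.** Section 4.6.1.1 sends the reader to Section 4.7 "for dose modification of lenalidomide and plamotamab in the instance of CRS". The Table 8 row refers back to Section 4.6.1.6, but only for managing signs and symptoms. Section 4.6.1.4 adds: "Management of CRS should be per standard investigational site procedures", and offers the protocol's approach where local standards are absent or incomplete. Section 7.10.1 says much the same.

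**The concern.** By Table 4, Grade 4 CRS means multiple vasopressors or positive-pressure ventilation. Whether a subject is redosed after that should not depend on which page the site opens. The table is the natural place to look for a dosing decision, and it is phrased as an instruction to give the next dose. The stop rule sits in guidance that the protocol offers as an alternative to site practice.

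A labelling problem adds to this. Section 10.2.3.1 grades both CRS and infusion reactions on the ASTCT CRS scale, and Section 4.6.1.3 notes that some manifestations are shared. Table 8 permanently stops plamotamab for a Grade 4 plamotamab infusion reaction but provides for redosing after Grade 4 CRS. The name given to the event could therefore decide whether the subject is redosed.

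What is at stake is subject safety and uniform conduct across sites. No efficacy endpoint, estimand or error rate depends on it.

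**Working it through.** **1. The two texts side by side**

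| Event | Section 4.6.1.6 | Table 8, CRS Grade 3 and 4 row | Agree? |
|---|---|---|---|
| First Grade 3 | Rechallenge allowed, per Table 8 | Next dose at 75% (100% allowed after C1D1) | Yes |
| Recurrence at Grade 3 | No further plamotamab | Permanent discontinuation | Yes |
| Recurrence at Grade 4 | No further plamotamab | Permanent discontinuation | Yes |
| First Grade 4 | No further plamotamab | Next dose at 75% (100% allowed after C1D1) | **No** |

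The conflict is confined to the last line.

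**2. Does Table 8 itself show what was intended?** It does not. Grade 4 plamotamab infusion reactions and Grade 4 neurotoxicity lead to permanent discontinuation. Grade 4 febrile neutropenia, and Grade 4 liver toxicity lasting no more than 3 days, allow resumption. Infusion reactions, neurotoxicity and liver toxicity each have their own Grade 4 row, so the merged CRS label is the table's own and not an effect of text extraction.

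**3. What the conflict means in dose**

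- Event on C1D1 (0.8 mg): Table 8 permits 100% × 0.8 = 0.8 mg again; Section 4.6.1.6 gives none.
- Event on a later dose: Table 8 gives 0.75 × 2 = 1.5 mg, 0.75 × 20 = 15 mg, 0.75 × 35 = 26.25 mg or 0.75 × 50 = 37.5 mg; Section 4.6.1.6 gives none. The 26.25 and 37.5 mg figures arise only at dose level 1 (Cohort 1B).

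**4. How often it might arise**

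The input is from Section 2.4.1: 4 of 80 NHL subjects had CRS of Grade 3 or higher, all with the first infusion.

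- Rate: 4/80 = 5.0%, exact (Clopper-Pearson) 95% CI 1.4% to 12.3%.
- The Grade 4 share is not reported. Assume 0 to 4 of the 4, so the Grade 4 rate is 0/80 = 0% to 4/80 = 5.0%.
- Among 40 planned Part 1 subjects: 40 × 0 = 0 to 40 × 0.05 = 2.0 expected.
- Among the 3 enrolled (SAP Section 1): 0 to 3 × 0.05 = 0.15 expected; chance of at least one, 0 to 1 − 0.95³ = 14.3%.
- After later infusions: 0/80 at Grade 3 or higher; one-sided 95% upper bound 1 − 0.05^(1/80) = 3.7%. This assumes that all 80 had a later infusion, which the protocol does not state.

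For the step-up regimen, Section 2.4.2 reports only Grade 1 or 2 CRS in 14 subjects, and Section 2.4.4 says the step-up regimen kept CRS at Grade 2 or below. The low end of these ranges is therefore the more plausible.

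**The case against.** The strongest reply is that the documents, read together, already point to discontinuation. Section 4.6.1.6 names Table 8, admits Grade 3 to it for rechallenge, and in the next sentence excludes any Grade 4. The Table 8 row points back to that section, and the opening of Section 4.7 refers readers to Section 4.6 for further guidance on CRS. On this view the only defect is a row label that is too broad. That is a fair account of probable intent. It does not remove the conflict: the row's own reference covers symptom management only, no sentence gives either text precedence, and someone using the table alone would redose.

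The remarks on site procedures are also weak evidence for either side. They concern treatment of the reaction, and Section 4.7 grants similar latitude. That point stands.

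The frequency figures are fairly criticised too. They rest on an assumed Grade 4 share and leave out sampling error. Taking the upper confidence limit as the Grade 4 rate would give 40 × 0.123 = 4.9 expected cases, and 1 − (1 − 0.123)³ = about 33% for at least one among 3. In the other direction, this trial adds two tafasitamab doses before C1D1, meant partly to mitigate CRS (Section 2.4.3). The closest data, 0/14, are too few to exclude much: the one-sided 95% upper bound is 1 − 0.05^(1/14) = 19%. The projections indicate scale only; the contradiction does not depend on them.

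Finally, there are safeguards. The Medical Monitor is notified immediately (Section 4.6.1.6) and must approve delays of over 14 days or 2 consecutive doses (Section 4.7). The investigator may withdraw a subject for an unacceptable AE (Section 6.3.1). Part 2 also required a protocol revision (Section 4.1.2), at which the row could have been corrected. These lower the risk, but none says which rule applies.

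**Conclusion.** The point holds. For a first Grade 4 CRS, the protocol both bars further plamotamab and provides for the next dose, and it sets no precedence. The wording of Section 4.6.1.6 favours discontinuation as the intent, but the documents do not settle it.

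The event is rare: on an assumed Grade 4 share of 0 to 4 of the 4 Phase 1 events, 0% to 5.0% of subjects, most likely near the low end for this regimen, and most likely at C1D1. With 3 subjects enrolled before termination, the present effect is small. The wording should still be corrected, because the protocol was written to treat at least 40 subjects in Part 1 and then Arm A of Part 2.

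**What to change.** Split the Table 8 CRS row in two.

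- **Grade 3:** keep the 75% rule, the 100% option after C1D1, the re-escalation steps and the present stop rule, limited to a first Grade 3 event.
- **Grade 4:** permanently discontinue plamotamab, matching Section 4.6.1.6.

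If the sponsor's safety team does intend rechallenge after Grade 4 CRS, Section 4.6.1.6 should be amended instead, with a justification.

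The cost is protocol wording in one table row. No extra subjects, visits or procedures are needed.

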	
Neutrophil count of 1,000/μL or less for at least 7 days OR
 
Neutrophil count of 1,000/μL or less with an increase of body temperature to 100.4°F (38°C) or higher OR
 
Neutrophil count less than 500/μL
	
 • Withhold plamotamab, tafasitamab, and lenalidomide and monitor CBC weekly until neutrophil count is 1,000/μL or higher. • Resume plamotamab and tafasitamab at the same dose and lenalidomide at a reduced dose. Refer to lenalidomide prescribing information for dosage modifications. • If recurrence, repeat drug withholding (first bullet above) and lenalidomide reduction steps until minimal lenalidomide dose is reached per lenalidomide prescribing information. • If recurrence at 5 mg lenalidomide, repeat drug withholding steps then reduce the next scheduled plamotamab dose to 75% of the previous dose.
Febrile Neutropenia	Grade 3 (severe) & Grade 4 (life-threatening)	
 • Withhold plamotamab, tafasitamab, and lenalidomide and monitor CBC until neutrophil count is Grade \leq 1. • Once subject is afebrile, off antibiotics and neutrophil count is Grade \leq 1, resume all therapy at the same dose and schedule.
Neurotoxicity	Grade 3 (severe)	
 • Withhold plamotamab and manage signs and symptoms (see Section 4.6.1.7) until the toxicity has recovered to \leq Grade 1 (mild) and has remained at \leq Grade 1 for at least 3 days before restarting therapy. • Reduce next scheduled plamotamab dose to 75% of the previous dose. If \geq Grade 2 toxicity does not recur, escalate plamotamab to full dose in subsequent administrations. • If \geq Grade 2 toxicity recurs at 75% dose, or if $<$ Grade 2 toxicity takes more than 7 days to resolve, permanently discontinue plamotamab. • Tafasitamab and lenalidomide dosing is not modified.
	Grade 4 (life-threatening)	
 • Stop infusion immediately, if still infusing and permanently discontinue plamotamab.
AST, ALT, bilirubin, and alkaline phosphatase in the absence of CRS	Grade 3 (severe)	
 • Withhold plamotamab and manage signs and symptoms until the toxicity has recovered to \leq Grade 1 (mild) or baseline. • If a Grade 3 liver toxicity persists $>$ 14 days and/or 2 consecutive doses are missed and the toxicity cannot be attributed to another cause, permanently discontinue plamotamab. • Tafasitamab and lenalidomide dosing is not modified.

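### After a first Grade 4 CRS, Section 4.6.1.6 stops plamotamab but Table 8 re-doses it, and no text says which governs

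*Protocol*

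**What the plan says.** **Protocol 4.6.1.6, Grade 3 and 4 block.** A subject with Grade 3 CRS or infusion reaction may be rechallenged after resolution, following Section 4.7 and Table 8. The permission names Grade 3 only. The next sentence reads: "Subjects with recurrent Grade 3 or any Grade 4 reaction should not receive further plamotamab treatment".

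**Protocol 4.7, Table 8, cytokine release syndrome.** One row carries the severity label "Grade 3 (severe) & Grade 4 (life-threatening" (final bracket cut). For both grades:

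- "The next scheduled dose of plamotamab will be given at 75% of the previous dose, unless the reaction occurred" on the C1D1 dose, "in which case 100% of the previous dose may be given".
- If the toxicity does not come back, or comes back at Grade 1, "escalate to full dose of plamotamab at the time of the next dose". If it comes back at Grade 2, stay at 75%.
- Permanent discontinuation applies only if toxicity recurs at or above "Grade 3 severity at any time or if a Grade 2 takes more than 10 days to resolve to" Grade 1 or lower.
- Lenalidomide is reduced after CRS of Grade 3 or higher; the tafasitamab dose is unchanged.

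**Cross-references.** Section 4.6.1.1 sends the reader to 4.7 for plamotamab and lenalidomide dose modification in CRS. The Table 8 row sends the reader back to 4.6.1.6 for managing signs and symptoms.

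**The concern.** A first Grade 4 CRS gets two different instructions: no further plamotamab, or a scheduled next dose. Table 4 defines Grade 4 CRS as needing multiple vasopressors or positive-pressure support, so this is a re-dosing rule after a life-threatening event. Section 4.6.1 says CRS is more likely after the first plamotamab dose than after later ones. Section 2.4.1 ties all four Phase 1 cases of Grade 3 or higher to the first infusion. That is also where Table 8 is most permissive, allowing the full previous dose again. A site working from the dosing table alone could re-dose a subject whom the treatment guideline would take off the drug.

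**Working it through.** **1. The two texts side by side, by event**

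| CRS event | Section 4.6.1.6 | Table 8 CRS row | Agree? |
|---|---|---|---|
| First Grade 3 | Rechallenge per 4.7 and Table 8 | Next dose 75% (100% allowed after C1D1) | Yes |
| Recurrent Grade 3 | No further plamotamab | Permanently discontinue | Yes |
| First Grade 4 | No further plamotamab | Next dose 75% (100% allowed after C1D1) | **No** |
| Grade 4 as a recurrence | No further plamotamab | Permanently discontinue | Yes |

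The conflict is confined to the third line.

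**2. Does the 4.6.1.6 sentence apply to CRS?** Yes. It stands in the CRS guideline and directly follows a sentence naming CRS and infusion reaction together. It cannot be read as covering infusion reactions only.

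**3. Does any text rank the two?**

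- 4.6.1.1 is a pointer to 4.7, without a statement that 4.7 prevails.
- 4.6.1.6 has its own pointer to Table 8, limited to Grade 3.
- Table 8 points back to 4.6.1.6, but for managing signs and symptoms.
- 4.6.1.4 and 4.7 defer to site practice for managing CRS; neither addresses whether plamotamab is given again.
- The SAP has no dosing rule.

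No precedence follows from these.

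**4. What each text gives after a first Grade 4 CRS.** Doses are from Table 3; the Table 8 factor is 0.75, or up to 1.00 after C1D1. Section 4.6.1.6 gives 0 mg in every case.

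| Dose at event | Table 8 |
|---|---|
| 0.8 mg (C1D1) | up to 0.8 × 1.00 = 0.8 mg |
| 2 mg | 2 × 0.75 = 1.5 mg |
| 20 mg | 20 × 0.75 = 15 mg |
| 35 mg (Cohort 1B) | 35 × 0.75 = 26.25 mg |
| 50 mg (Cohort 1B) | 50 × 0.75 = 37.5 mg |

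**5. How many subjects?** The documents give no Grade 4 CRS count. The nearest figures are:

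- Grade 3 or higher, Phase 1 NHL (2.4.1): 4/80 = 5.0%. Clopper-Pearson 95% limits are the 0.025 quantile of Beta(4, 77) = 0.0138 and the 0.975 quantile of Beta(5, 76) = 0.1231, so 1.4% to 12.3%.
- Flat-dose cohort (2.4.2): 0/14. Upper limit 1 − 0.025^(1/14) = 0.2316, or 23.2%.

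For the minimum of 40 Part 1 subjects, 0.05 × 40 = 2 events of Grade 3 or higher, and at the 4/80 upper limit 0.1231 × 40 = 4.9. Grade 4 is an unknown part of these. The 5% is a point estimate and should not be read as a ceiling.

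**The case against.** The best defence is that a careful reader ends up safe. The 4.6.1.6 rule is grade-specific, sends only Grade 3 to Table 8, and is itself cited in the Table 8 row. Stopping is always open to the investigator, since 6.3.1 allows withdrawal from treatment for an unacceptable AE. The Medical Monitor must be told at once (4.6.1.6). Under 4.7, a toxicity above Grade 2 that prevents dosing for more than 14 days, or two consecutive missed doses, may require discontinuation, and such delays need Medical Monitor approval. Many Grade 4 cases could reach that check during weekly dosing. All of this stands as mitigation. None of it says which text governs a first Grade 4 event, and a subject who recovers quickly would not trigger the delay check.

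Four stronger readings may tempt a reader, and the documents do not support them:

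- *Investigators are trapped by the no-deviation rule in 12.2.* Both sections are titled as guidelines, the bar says should not, and 6.3.1 always permits stopping.
- *The merged row is plainly a drafting slip.* Table 8 does stop plamotamab after a Grade 4 infusion reaction ("Plamotamab if during or immediately following plamotamab infusion") and Grade 4 neurotoxicity ("Stop infusion immediately, if still infusing and permanently discontinue plamotamab"). But its combined Grade 3 and 4 febrile neutropenia row resumes all therapy at the same dose, and Grade 4 liver toxicity ends treatment only if it lasts more than 3 days. Grade 4 is not a uniform stop in the table, so a slip is an inference.
- *The label, CRS or infusion reaction, decides whether a subject is re-dosed.* That split appears only if Table 8 is read without 4.6.1.6, whose bar covers both. Section 4.6.1.3 also treats the two as mechanistically different.
- *The trial's results are affected.* They are not: the SAP (Sections 1, 4.1 and 7) reports early termination with 3 subjects and listings only.

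**Conclusion.** The inconsistency is real and narrow. For a first Grade 4 CRS the protocol both bars further plamotamab and schedules it, with no rule of precedence. It should be corrected because the event is life-threatening and the correction costs almost nothing. Per event, the difference is 0 mg against 75% of the previous dose, or up to 100% after C1D1. Few subjects would be affected, possibly none. That judgement assumes that Phase 1 monotherapy rates carry over to the triple combination. Section 4.6.1.1 warns that lenalidomide may potentiate CRS, while the tafasitamab run-in and step-up dosing are meant to reduce it, so the true rate could lie either way. No sample size, error rate or planned analysis depends on this point. The documents do not show which text the sponsor intended; the fix takes the more protective one.

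**What to change.** Split the Table 8 CRS row in two.

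- *Grade 3, first event:* keep the present text, with rechallenge at 75% (100% allowed if on C1D1) and the existing recurrence rules.
- *Grade 4:* stop the infusion, manage per 4.6.1.6, permanently discontinue plamotamab; tafasitamab dose not modified.

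The sponsor should also state whether the lenalidomide reduction for CRS still applies once plamotamab has been stopped. Section 4.6.1.1 grounds that caution in the combination with plamotamab, yet for events after the first five plamotamab doses Table 8 reduces all later lenalidomide doses. Carrying the reduction over without comment could leave a subject on less lenalidomide after its stated reason has gone.

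If the sponsor did intend re-dosing after a first Grade 4 CRS, the alternative is to amend 4.6.1.6 to say so and justify it.

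The cost is one split table row and one clarifying sentence, with no added visits, assessments or subjects. As enrolment has ended, the change matters for the record and for any later protocol that reuses this text.
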